- d. Vital signs are assessed predose. Height is measured at Screening only.
- e. Blood samples for tuberculosis (Quantiferon) testing will be obtained at Screening. Additional samples should be taken for viral serology testing at Screening: HBV antibodies, HbsAg, and HCV antibodies. HIV testing will be done at Screening only where required as per local regulations.
- f. Randomization should occur on Day 1 after all Screening procedures have been completed; participant eligibility must be reviewed again and confirmed at the site on Day 1 prior to randomization.
- 9 Blood samples for hematology and chemistry (Table 8) to be obtained at Screening, predose at all Visits when collected except Day 1.
- h. For participants in the placebo/M2951 arms, supplemental LFT monitoring (Table 8) will be conducted, and additional samples drawn.
- Samples for total Ig levels (IgM, IgA, IgG) will be obtained predose (see Section 7.4.5).
- Urine samples for urinalysis will be obtained at Screening, predose at Weeks 12, 24, 48, and 52. If local urinalysis by dipstick is abnormal, urine microscopy should be performed by a central laboratory. If at least 1+ protein is detected, urine protein/creatinine ratio should be determined.
- Blood samples for CCI CCI CCI Will be obtained predose. An additional sample will be collected at the 4-week Safety Follow-up/End of Trial Visit (see Sections 7.4.6 and 7.6.3).
- Serum pregnancy test collected at Screening, and urine tests collected predose at every monthly trial visit, for women of childbearing potential only. Urine pregnancy tests will also be performed at home/site at Weeks 28, 32, 40, and 44 for women of childbearing potential randomized to the M2951/placebo arm. If necessary to confirm postmenopausal status, FSH testing will be done at Screening in postmenopausal women.
- m. Phone calls: To be done only if urine pregnancy test is completed at home. Participants will be supplied with at-home test kits. The Principal Investigator and/or delegated site staff will call participant at Weeks 28, 32, 40, and 44 to confirm completion of home pregnancy testing and discuss results.
- n. ECG and posteroanterior CXR performed at Screening. Participants who have previously had a CXR for clinical reasons within 3 months prior to Day 1 do not need to have the CXR repeated if the results are available and show no sign of active infective process or any other clinically significant abnormalities. ECGs will also be conducted at Weeks 24 and 48.

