7.1.2 Treatment Visits, Including Blinded Treatment Extension Phase

At all trial visits, scheduled assessments will be performed before administration of the trial medication, with the exception of relevant blood draws (e.g., CC) as noted in Table 1). After Day 1, all scheduled visits during the treatment period may take place within ± 3 days of the protocol-specified day. Participants who discontinue early must immediately return for the 4-week Safety Follow-up/End of Trial Visit (see Section 7.1.8).

See Table 1 for specific assessments to be done during treatment periods.

The following will be performed on Day 1:

- Review of inclusion/exclusion criteria;
- Randomization:
- CCI
- Review of concomitant medications and procedures, evaluation of AEs, disease activity assessment (EDSS), vital signs, and a neurologic exam;
- Blood sample collection for Ig levels, CCI
 CCI
- Urine collection for a urine pregnancy test (women only);
- IMP dispensation;

The following will be performed at Week 4, 8, 12, 16, 20, 24, and 36:

- CCI
- Review of concomitant medications and procedures; evaluation of AEs; disease activity assessment (relapse assessment, EDSS [Week 12, 24, and 36 only]); a complete physical examination (Week 12 and 24 only); vital sign assessment; and a neurologic exam;
- IMP compliance;

- 12-lead ECG (Week 24 only);
- Blood sample collection for safety assessments (hematology, chemistry); Ig levels (Week 4, 16, and 24 only); CCI cell count and CCI
- Blood tests (ESR, hsCRP, and fibringen) at Week 36;
- Urine collection for urine pregnancy testing (women only); urinalysis and, if necessary, microscopy and protein:creatinine ratio (Weeks 12 and 24 only);

The following will be performed at Weeks 28, 32, 40, and 44 for women of childbearing potential: urine pregnancy testing will be performed at home or at the site. Urine pregnancy test kits will be provided to the participant at Week 24 (for testing at Weeks 28 and 32) and at Week 36 (for testing at Weeks 40 and 44). At and/or prior to the Week 24 Visit, the Principal Investigator and/or delegated site staff will train the relevant participants to self-administer the urine pregnancy test, and will contact the participant by telephone at Week 28 (\pm 3 days), 32 (\pm 3 days), 40 (\pm 3 days), and 44 (\pm 3 days) to confirm completion of urine pregnancy testing and discuss results.

- MRI assessment (Weeks 12, 16, 20, and 24 only);
- IMP dispensation.

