7.1.3 Supplemental Safety Visits

Additional chemistry monitoring (including ALT, AST, alkaline phosphatase, γ -glutamyl-transferase, and bilirubin) will be conducted every 2 weeks until 16 weeks of treatment with evobrutinib (or an increase in the dose of evobrutinib). Subsequently, this will be conducted monthly (every 4 weeks). In the OLE, participants crossing over from the Tecfidera arm to M2951 will have additional safety monitoring conducted as described below.

- In the main study, for all participants in the placebo/M2951 arm, safety visits will be conducted every 2 weeks until Week 40, then monthly at Weeks 44 and 48 (see Table 1).
- During the first 2 years of the OLE period, safety visits will be conducted every 2 weeks until Week 16, then monthly at Weeks 20, 24, 28, 32, 36, 40, 44, 48, 52, 56, 60, 64, 68, 72, 76, 80, 84, 88, 92, and 96 (see Table 2). Subsequently, participants will attend the study site or have a Telephone Visit at least every 6 weeks (see Table 3).
- During the OLE period, additional safety visits will be conducted for participants crossing over from the Tecfidera arm at Weeks 1, 3, 5, 7, 9, 11, 13, and 15.

Safety visits will be conducted after obtaining participant's informed consent. These safety evaluations have been implemented by a letter to Investigators as an urgent safety measure. Given the current status of most participants, these evaluations will start after Week 1 of OLE. It is preferable for chemistry monitoring to be performed at the Investigator's site.

An

additional physical examination may be performed at the Investigator's discretion based on the participant's history at the time of the visit. Any new or change in AEs and concomitant medications should be documented. Patient compliance to additional safety monitoring will be overseen to evaluate continuation in the trial.

These visits should be done at the Investigator's site and blood samples sent to Central Laboratory. In the event that the participant cannot return to the site for the additional blood draws, chemistry monitoring should be done locally; any participants completing a supplemental safety visit locally will not have **CC** collected at that visit.

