7.1.5 End of Treatment Visit

The following will be performed at Week 48 ± 3 days/End of Treatment Visit (for participants who do not continue in the OLE or participants who received Tecfidera during the 48-week main study and choose to participate in the OLE):

CCI

- Review of concomitant medications and procedures, evaluation of AEs, disease activity assessment (relapse assessment, EDSS), vital signs, and a neurologic exam;
- IMP compliance;
- 12-lead ECG;
- Blood sample collection for safety assessments (hematology, chemistry, coagulation); Ig levels; CCl and CCl ;
- Urine collection for urinalysis and, if necessary, microscopy and protein:creatinine ratio; urine pregnancy testing (women only);
- MRI assessment.

Participants who complete 48 weeks of treatment with M2951 or Tecfidera (and do not withdraw early) will be given the opportunity to participate in the OLE Period. Participants who enter the OLE from Tecfidera will sign the OLE ICF at this visit.

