- (ALT or AST) ≥ 3×ULN, (ALT or AST) ≥ 5×ULN, (ALT or AST) ≥ 10×ULN, (ALT or AST) ≥ 20×ULN
- TBILI ≥ 2×ULN
- Concurrent AST ≥ 3×ULN and TBILI ≥ 2×ULN
- Concurrent ALT \geq 3×ULN and TBILI \geq 2×ULN
- Concurrent (ALT or AST) $\geq 3 \times ULN$ and TBILI $\geq 2 \times ULN$
- Concurrent (ALT or AST) $\geq 3 \times ULN$ and TBILI $\geq 2 \times ULN$ and ALP $\geq 2 \times ULN$
- Concurrent (ALT or AST) $\geq 3 \times ULN$ and TBILI $\geq 2 \times ULN$ and ALP $\leq 2 \times ULN$ or missing

Concurrent measurements are those occurring on the same date.

Categories will be cumulative, i.e., a participant with an elevation of AST \geq 10×ULN will also appear in the categories \geq 5×ULN and \geq 3×ULN.

ALT values over time will be presented in a spaghetti plot for participants with on-treatment ALT grade 2 or higher elevation (i.e. grade \geq 2) during the OLE period, by treatment group. There will be 1 panel by treatment group. All plots by parameter will have the same scales to allow comparison between groups.

Kaplan-Meier estimates of proportion surviving event-free as a function of time will be presented for the following 4 types of events based on the ALT and eGFR parameters:

- Time from OLE first dose to first occurrence of ≥ grade 2 ALT (days) (for participants with OLE baseline grade < 2)
- Time from OLE first dose to first increase in ALT ≥ 1 grade above OLE baseline grade (days)

- Time from first Evobrutinib dose to first increase in ALT ≥ 2 grade above baseline grade (days) in DBP+OLE
- Time from first Evobrutinib dose to first increase in ALT ≥ 3 grade above baseline grade (days) in DBP+OLE.
- Time from OLE first dose to first occurrence of eGFR assessment equal to less than (<) 60 mL/min for participants with OLE baseline eGFR ≥ 60 mL/min by treatment group (days)

For the above figures based on OLE: time-to-event figures will be based on data from OLE weeks 0-end of treatment; a participant reaching end of treatment, without experiencing the event will have his/her event time right-censored at the time of the last ALT/eGFR assessment. A separate KM curve will be estimated for each of the 5 initial groups: Placebo + Evobrutinib 25 mg QD, Evobrutinib (any dose) and Tecfidera. For the figures based on DBP+OLE: the start time will be the first Evobrutinib dose irrespective of its occurrence during DBP or OLE phase.

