- 2. Abnormalities in lipase and amylase (i.e. higher the ULN). For the DBP information to be displayed by original treatment groups. For the OLE period only "Total" is needed.
- 3. Summary of potential DILI by R-Values and Periods for subjects with any ALT or AST elevation for DBP+OLE.

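### Liver tests are scheduled less often for Tecfidera than for the other arms in the main study, and more often early in the OLE, so any-elevation results by group can differ through sampling alone

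*SAP*

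**What the plan says.** **Main-study testing.** Chemistry is drawn in every arm at the visits that Protocol 7.1.2 introduces with "The following will be performed at Week 4, 8, 12, 16, 20, 24, and 36", and again at Week 48 (Protocol 7.1.5). The supplemental liver tests are for some arms only. Table 1, footnote h, states: "For participants in the placebo/M2951 arms, supplemental LFT monitoring (Table 8) will be conducted, and additional samples drawn". For those arms, Protocol 7.1.3 sets the frequency: "safety visits will be conducted every 2 weeks until Week 40, then monthly at Weeks 44 and 48".

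**OLE testing.** All participants are tested every 2 weeks to Week 16. In addition, "additional safety visits will be conducted for participants crossing over from the Tecfidera arm at Weeks 1, 3, 5, 7, 9, 11, 13, and 15" (Protocol 7.1.3). The OLE biochemistry windows in SAP Appendix 3 show the same split.

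**Outputs.** SAP 17.3 includes a "Summary of potential DILI by R-Values and Periods for subjects with any ALT or AST elevation for DBP+OLE". That item names no grouping, so the SAP 11.1 default applies: five initial groups plus Total. For the OLE time-to-event figures on ALT, SAP 17.3 says "A separate KM curve will be estimated for each of the 5 initial groups". The liver-test category table is by treatment group and covers the OLE only.

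**What is absent.** The visit windows in SAP 11.13 and Appendix 3 organise by-visit summaries. Nothing in SAP 17.3 adjusts an any-elevation or first-elevation output for the number of tests, restricts it to shared visits, or adds a caveat.

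**The concern.** Whether a participant ever shows an elevation depends on the true course of ALT and on how often it is measured. A group tested less often will tend to show fewer transient elevations, and to show them later, even when the underlying risk is the same.

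Here the imbalance changes direction. Tecfidera is tested less than the others in the main study and more than the others in the first 16 OLE weeks, which is when its participants first take evobrutinib. A summary split by period would show both effects. Drug-induced liver injury is the important identified risk in Protocol 3.2, so these columns will be read closely even though no formal comparison with Tecfidera is planned.

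**Working it through.** **Step 1. Count the scheduled on-treatment tests (Protocol Tables 1 and 2, Section 7.1.3).**

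| Period | Tecfidera group | Placebo/M2951 groups |
|---|---|---|
| Main study | Weeks 4, 8, 12, 16, 20, 24, 36, 48 = 8 | Weeks 4, 8, every 2 weeks from 10 to 40, 44, 48 = 20 |
| of which after Week 24 | 36, 48 = 2 | 10 |
| OLE Weeks 1 to 16 | weekly = 16 | even weeks = 8 |

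In each period the sparser schedule is a subset of the denser one.

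**Step 2. Check the count against the plan's own figure.** Appendix II gives at least 23 blood-draw days in the main study. Screening 1 + Day 1 1 + 20 + Week 52 1 = 23, which matches the placebo/M2951 schedule. The same sum for Tecfidera is 1 + 1 + 8 + 1 = 11.

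**Step 3. Chance that one elevation meets a scheduled test.** Assume an elevation of D weeks with uniform onset over T weeks, and gaps g between tests. The chance is the sum of min(g, D) divided by T. The documents do not give D, so it is an assumption.

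- Tecfidera gaps: six of 4 weeks, two of 12 weeks.
- Placebo/M2951 gaps: four of 4 weeks, sixteen of 2 weeks.

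| D (weeks) | Tecfidera, Weeks 0–48 | Placebo/M2951, Weeks 0–48 |
|---|---|---|
| 2 | 16/48 = 33% | 40/48 = 83% |
| 4 | 32/48 = 67% | 48/48 = 100% |
| 8 | 40/48 = 83% | 100% |
| 12 | 48/48 = 100% | 100% |

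For onset in Weeks 24 to 48 and D = 4: Tecfidera (4 + 4)/24 = 33%; placebo/M2951 100%.

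In OLE Weeks 1 to 16, D = 1 gives 100% for former Tecfidera participants and 50% for the others. D of 2 weeks or more gives 100% for both.

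**Step 4. Mean delay from onset to next test,** sum of g² divided by 2T:

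- Main study, Tecfidera: (6×16 + 2×144)/96 = 4.0 weeks.
- Main study, placebo/M2951: (4×16 + 16×4)/96 = 1.33 weeks.
- OLE: 16/32 = 0.5 week for former Tecfidera participants and 32/32 = 1.0 week for the others.

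**Step 5. Noise illustration with no drug effect.** All parameters are assumed: ALT median 0.5×ULN, between-person log SD 0.4, within-person CV 20%. The chance of any value above ULN in the main study is about 16% with 8 tests and 22% with 20. Among participants whose baseline is at or below ULN it is 11.6% and 17.0%. Over medians of 0.4 to 0.6×ULN and CVs of 15 to 30%, the ratio runs from 1.22 to 1.52 without the baseline condition and from 1.37 to 1.60 with it. At 3×ULN the chances are about 0.01% to 0.03%, and at the noisiest corner (0.6×ULN, CV 30%) 0.36% against 0.71%. For the OLE to Week 16 (log SD 0.35, baseline at or below ULN), any value above ULN occurs in about 10% with 8 tests and 14% with 16.

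**Step 6. Which outputs each contrast reaches.** The 8-against-20 contrast enters the DBP+OLE R-value summary. It does not enter the ALT Kaplan-Meier figures, which start at the first OLE dose or the first evobrutinib dose, or the OLE-only category table. There the early-OLE contrast of 16 against 8 applies. In the ALT figures timed from first evobrutinib dose, the scheduled tests in the first 16 weeks are 6 (M2951 arms), 8 (placebo, from Week 24) and 16 (Tecfidera), but those figures need a rise of at least 2 or 3 grades.

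**Step 7. What a common-visit restriction can lose.** Under Protocol 6.4.4.1, M2951 is interrupted or stopped for ALT or AST above 3×ULN. Suppose an elevation that would last 12 weeks starts uniformly in Weeks 24 to 48, is first seen at a supplemental visit, and resolves R weeks after stopping. It is then visible at the Week 36 or Week 48 visit as follows:

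- R = 2: onset in (32, 36] or (44, 48], 8/24 = 33%.
- R = 6: onset in (28, 36] or (40, 48], 16/24 = 67%.

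The same 12-week elevation in Tecfidera is always visible at one of those visits.

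**The case against.** The case against acting is substantial, and much of it stands.

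- **The controlled comparison is sound.** A reader might infer that placebo against M2951 is biased in the main study. The documents do not support that, because all four arms share one schedule. Only open-label Tecfidera differs, and Protocol 8.5.4 rules out formal safety comparisons with it.
- **Scope is narrow.** A reader might infer that 8 against 20 affects every liver output. Among the outputs examined here it reaches only the R-value summary, whose by-group layout comes from a default. SAP 17.3 does not define the elevation threshold for that item.
- **The OLE effect is small.** A reader might expect sampling to make former Tecfidera participants look clearly worse. Elevations of 2 weeks or more are caught equally. These participants are also starting evobrutinib while the others have already taken it, so a real early difference is plausible and no visit filter makes the groups comparable.
- **High thresholds are barely touched by noise,** as Step 5 shows.
- **Counts are scheduled, not actual.** The two-weekly visits arrived with Amendment 1 in November 2017, after a planned first participant in Q2 2017, and were revised later. The real imbalance is unknown and may be smaller.
- **A restricted analysis could hide true events.** Step 7 bears this out and limits the remedy.

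What does not stand is that descriptive status disposes of the matter. It removes any type I error question, but an unadjusted any-elevation column can still mislead.

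**Conclusion.** The point holds in limited form. The schedules differ by 8 against 20 in the main study and 16 against 8 in OLE Weeks 1 to 16, the SAP shows results by group, and it makes no allowance for this. Any-elevation results can therefore differ between Tecfidera and the other groups with no difference in risk.

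The main-study effect can be large for short elevations and is absent at 12 weeks or more. In the OLE it is confined to near-threshold or under-2-week elevations and a shift of about half a week in first detection, mainly in the figure for a rise of at least one ALT grade. These sizes rest on the current schedule being followed and on assumed durations and ALT variability. Sample size, power and alpha play no part.

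A reader might go further and conclude that the common-visit version should become the one used to compare groups. The documents do not support that. The M2951 stopping rules act on supplemental tests, so that version can under-count evobrutinib events, finding 33% to 67% against 100% in the Step 7 example.

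**What to change.** 1. Keep the all-tests outputs as the main safety display, including Total and listings.
2. Add a supportive by-group version of the R-value summary and of the OLE Kaplan-Meier figure for a rise of at least one ALT grade, using only visits scheduled for every group: main-study Weeks 4, 8, 12, 16, 20, 24, 36 and 48; OLE even weeks to Week 16, then the common schedule. Scheduled tests become 8 against 8 in both periods.
3. Show the number of liver tests per participant by group and period. This also reveals the actual imbalance.
4. State that a Tecfidera difference is not attributed to the drug unless both versions agree.
5. State in the SAP which elevation threshold and which periods the R-value summary uses.

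**Cost.** A visit filter, two repeated outputs and one count table; no change to trial conduct. The downside to print with the supportive version is that it can under-count elevations found at supplemental visits that led to interruption or discontinuation, so it must not replace the all-tests version.

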17.4 Vital Signs

The SAF-OLE analysis set will be used in presenting the vital signs results. Vital signs (height (cm), weight (kg), BMI (kg/m²), body temperature (°C), Systolic Blood Pressure (SBP) (mmHg), Diastolic Blood Pressure (DBP) (mmHg), respiratory rate (breaths/min) and pulse rate (beats/min)) will be summarized by treatment group using descriptive statistics (see Section 11.5).

The descriptive statistics will be presented as follows:

- · The OLE baseline will be presented first
- Then each scheduled time point will be presented on participants who have reached this time
 point: absolute values and OLE CFB will be displayed (except for height and BMI as they are
 only present at screening visit).

Body temperature, SBP, DBP, respiratory rate and pulse rate will be analyzed with shift tables of maximum CFB using the categories defined in Table 5:

Table 5: Vital Signs Categories

Parameter	Unit	Shift	Baseline categories	Post-baseline categories (absolute change)
Temperature	°C	Increase	<37 / ≥37 - <38 / ≥38 - <39 /≥39 - <40 / ≥ 40	≤0* / >0 - <1 / ≥1 - <2 /≥2 - <3 / ≥3
Pulse rate	1 '	Increase and decrease	<100 / ≥100	≤0*/>0 - ≤20/>20 - ≤40/>40
SBP	9	Increase and decrease	<140 / ≥140	≤0* / >0 - ≤20 / >20 - ≤40 / >40
DBP		Increase and decrease	<90 / ≥90	≤0*/>0-≤20/>20-≤40/>40
Respiratory rate		Increase and decrease	<20 / ≥20	≤0* / >0 - ≤5 / >5 - ≤10 / >10

^{*} This category will include the participants with no changes or decrease/increase in the increase/decrease part of the table respectively.

In addition, 2 scatter plots on OLE period will be provided presenting:

- OLE baseline SBP value versus maximum (highest) post-baseline SBP value
- OLE baseline Diastolic BP value versus maximum (highest) post-baseline Diastolic BP value

Line for linear regression will be included. The figures will be produced overall, i.e., for all participants pooled.

A listing of maximum CFB for OLE period and a listing of all vital signs data for OLE period will be provided.

17.5 12-Lead Electrocardiogram (ECG)

The 12-lead ECG data will be listed and summarized for the OLE period for observed values and change from OLE baseline values by treatment group using descriptive statistics:

- Ventricular rate (beats/min)
- Pulse rate interval (msec)
- QRS (msec)
- QT (msec)
- Fridericia corrected QT (QTcF) (msec).

The QTcF parameter will be categorized by observed value into the categories

- \leq 430 msec,
- > 430 450 msec,
- > 450 480 msec.
- > 480 500 msec,
- > 500 msec

and by CFB value into the categories

- \leq 30 msec,
- > 30 60 msec,
- > 60 msec.

Number and percentage of participants within each category listed above, based on their post-OLE baseline QTcF data, will be presented by treatment group.

A shift table of rhythm results (Sinus rhythm, Atrial fibrillation, Other, Missing) from OLE baseline to last on treatment category, presented by treatment group, will be provided for the OLE period.

Shift tables of morphological assessments (Normal, Abnormal, Missing) from OLE baseline to maximum on treatment value will be provided for the OLE period.

Listings of ECG quantitative values, morphological and rhythm results will be produced on OLE period.

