7.4.4.2 Physical Examinations

Physical examinations will be assessed at each site as indicated in Table 1, Table 2, and Table 3. Physical examination includes assessment of the following: general appearance, skin, head and neck, mouth, lymph nodes, thyroid, abdomen, and musculoskeletal, cardiovascular, and respiratory systems. Physical examination findings during Screening before obtaining informed consent will be recorded as medical history events and new findings or worsening during the trial as AEs. Records from physical examinations will be retained at each site and will not be captured in the eCRF.

7.4.4.3 12-Lead ECG and Chest X-ray

A 12-lead ECG will be performed during Screening. For participants in the OLE Period, a 12-lead ECG will also be conducted at OLE Day 1, unscheduled visits, Week 48, and then every 48 weeks

up to and including the OLE End of Treatment Visit. The 12-lead ECG recordings will be obtained after 10 minutes of rest in a semisupine position.

The following ECG parameters will be obtained directly from the computerized 12-lead ECG recordings: rhythm, ventricular rate, PR interval, QRS duration, and QT interval. The corrected QT interval will be calculated using Fridericia's formula. The overall evaluation (normal/abnormal) will be recorded on the eCRF, and if abnormal, the specific abnormality will be recorded. Abnormal evaluations will be judged as clinically significant or not clinically significant by the Investigator.

The printout of the ECG is to be signed, dated, and filed in the Investigator's Site File along with a signed and dated copy (if the printouts are not on archive-quality paper).

Posteroanterior CXRs will be performed during Screening according to local standard practice. For participants in the OLE Period, a CXR will be performed at OLE Day 1. Participants who had a CXR performed for clinical reasons within 3 months prior to Day 1 do not need to have the CXR repeated. The CXR should show no evidence of active infective process, or any other clinically significant abnormalities. The overall evaluation (normal/abnormal) will be recorded on the eCRF, and if abnormal, the specific abnormality will be recorded. Abnormal evaluations will be judged as clinically significant or not clinically significant by the Investigator.

[figure not shown]
The 12-lead ECG and CXR will be performed and read locally.

[figure not shown]

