11.2 Presentation of Tables/Listings/Figures

TLFs will be presented using initial treatment groups (i.e., true treatment groups as "Placebo+Evobrutinib 25 mg QD", "Evobrutinib 25 mg QD", "Evobrutinib 75 mg QD", "Evobrutinib 75 mg BID", and "Tecfidera") and total population. A footnote will be added to indicate that participants switched from Placebo to Evobrutinib 25 mg QD for the second 24-week treatment period. A second footnote will be added to indicate that all participants switched to Evobrutinib 75 mg QD on OLE Week 0 and following protocol amendment V5 dated 21 November 2018, all participants still ongoing in OLE switched to Evobrutinib 75 mg BID.

All data recorded during the trial will be presented in individual data listings performed on the Safety OLE Analysis Set (SAF-OLE), unless otherwise specified. All listings will be sorted by treatment group, participant, and scheduled time point (where applicable), if not otherwise stated. Further details are provided in the appropriate section for the analysis of the specific parameter.

Tables and figures will be presented by treatment group and scheduled time point during OLE period (where applicable), unless otherwise specified. Tables and figures will be sorted by treatment group and chronological scheduled time point (where applicable).

Summary statistics as displayed in tables and figures will include data until end of study.

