17.7 Pregnancy Test

Results of pregnancy test (urine or serum) will be listed for OLE period based on SAF-OLE.

Analyses will be performed for the DBP+OLE period based on the SAF analysis set and for OLE period based on the SAF-OLE.

Data on immunoglobulin (Ig) levels, and CCl (see list of parameters in Appendix 19.2) will be summarized for the OLE period for observed values, change from OLE baseline values, and percent change from OLE baseline by treatment group and overall using descriptive statistics.

In addition, number and percent of subjects falling above, below, and within normal range will be summarized where applicable. Assessments made at the End of Treatment visit for treatment discontinuers will be windowed appropriately. Assessments made at the End of Trial visit for study discontinuers will be summarized separately from assessments made at Safety follow-up visit at OLE Week 388 End of Trial visit for study completers.

Additionally, descriptive statistics of absolute values of CCI will be provided for subjects falling above, below, and within normal range of the specific laboratory parameter. Summaries will be provided on OLE period for observed values, change from OLE baseline values, and percent change from OLE baseline by treatment group and overall.

Shift tables from OLE baseline value (low, normal, high) to end of OLE Period will be presented by treatment group and overall, for each Ig class and subclass, and parameters where applicable (see list of parameters in Appendix 19.2), using SAF-OLE analysis set.

[figure not shown]
Boxplots for each Ig class and subclass, (g/L), and CC (see list of parameters in Appendix 19.2) by treatment group and time point will be provided, for OLE period.

Line plots of median percent change from baseline will be provided by time point and treatment group on DBP and OLE combined periods for each Ig class and subclass, and (see list of parameters in Appendix 19.2).

(see list of parameters in Appendix 19.2) and Ig class and subclass levels will be listed by treatment group, participant and time point (where applicable). IgG values < 3 g/L (severe hypogammaglobulinemia) and IgG values < 6 g/L (hypogammaglobulinemia) will be flagged in the listing.

EAIR of infections

For definition of severe infections AESI, see Section 17.2.3 and Appendix 19.5.

Confidence interval of incidence rate will be calculated using the Garwood method for Poisson mean.

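### SAP 17.5 tabulates ECG rhythm only at the last on-treatment ECG, so atrial fibrillation that resolves earlier is absent from the ECG summary tables

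*SAP*

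**What the plan says.** SAP 17.5 specifies the rhythm output as "A shift table of rhythm results (Sinus rhythm, Atrial fibrillation, Other, Missing) from OLE baseline to last on treatment category", by treatment group. The next sentence specifies "Shift tables of morphological assessments (Normal, Abnormal, Missing) from OLE baseline to maximum on treatment value". The descriptive ECG summary in the same section covers rate and interval parameters only. Beyond the shift table, rhythm appears in listings: "Listings of ECG quantitative values, morphological and rhythm results will be produced on OLE period".

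On the schedule, Protocol 7.4.4.3 states that "a 12-lead ECG will also be conducted at OLE Day 1, unscheduled visits, Week 48, and then every 48 weeks". The series closes with an ECG at the visit that ends OLE treatment.

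For immunoglobulins (Ig), SAP 17.8 plans "Shift tables from OLE baseline value (low, normal, high) to end of OLE Period will be presented by treatment group and overall". It also states that "number and percent of subjects falling above, below, and within normal range will be summarized where applicable", and it plans boxplots and median percent-change plots by time point and a listing that flags IgG below 6 g/L and below 3 g/L.

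**The concern.** A safety shift table should show whether an abnormality appeared on treatment. The rhythm table names atrial fibrillation as a category but reads each participant's rhythm at one ECG, the last. Atrial fibrillation can come and go, and a last-value rule does not register an episode that has ended. ECGs are a named OLE safety endpoint (Protocol 8.3.4), and the OLE objective includes long-term safety (Protocol 4.4). Someone who reads the tables and not the listings could conclude that no participant developed atrial fibrillation when some had.

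The Ig shift table also uses a single late value, so it calls for the same check.

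**Working it through.** No planned figure depends on this rule, so the check is a comparison of the SAP's rules followed by a count of assessments.

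**1. Post-baseline value used in each shift table**

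| Shift table | SAP section | Post-baseline value |
|---|---|---|
| Hematology, biochemistry | 17.3 | worst value; worst grade |
| Vital signs | 17.4 | maximum change |
| ECG morphology | 17.5 | maximum |
| ECG rhythm | 17.5 | last |
| Ig | 17.8 | end of OLE |
| C-SSRS | 17.10 | worst (maximum score) |

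Only rhythm and Ig depart from the pattern, and no reason is given. The worst-value rule of 17.3 cannot be assumed to cover Ig. Protocol Table 8 places Ig under hematology, but SAP Appendix 19.1, which sets the worst direction for each parameter, does not list it.

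**2. Trace of one case.** Take sinus rhythm at OLE baseline, atrial fibrillation at OLE Week 96 and sinus rhythm at the last ECG.
- Rhythm shift table: sinus to sinus.
- Descriptive ECG summary: rhythm is not included.
- Morphology shift table: Abnormal, if that ECG was so assessed. The category does not identify atrial fibrillation.
- Listing: shown.
- Adverse event tables: counted only if the finding came with signs or symptoms, led to stopping treatment, or was judged medically important (Protocol 7.4.1.1). Atrial fibrillation is not among the events of special interest (SAP 17.2.3), so it has no dedicated summary.

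SAP 11.11 brings unscheduled data into shift analyses, and Protocol 7.1.4 includes an ECG at unscheduled neurological visits. Under the last-value rule such an ECG counts only if it is the last one.

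**3. Number of scheduled ECGs.** Protocol Tables 2 and 3 give post-baseline OLE ECGs at Weeks 48, 96, 144, 192, 240, 288, 336 and 384, so k = 8. The ECG windows in SAP Appendix 19.3 stop at Week 336, so k = 7.

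**4. Illustrative miss rate.** Assume the finding is present at exactly one of k scheduled ECGs and is equally likely at each. The table shows it only if that ECG is the last, so the probability of a miss is 1 − 1/k.
- k = 7: 1 − 1/7 = 0.857, or 86%.
- k = 8: 1 − 1/8 = 0.875, or 87.5%.

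If the rhythm, once present, persists to the last ECG, the miss is 0%.

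**5. Immunoglobulins.** OLE samples fall on Day 1 and every 24 weeks to Week 384: 1 + 384/24 = 1 + 16 = 17. At 5 mL each this is 85 mL, which reproduces the 17 samples and 85 mL in Protocol Appendix II. On the assumption of step 4, the end-of-OLE shift table alone would miss an isolated low value with probability 1 − 1/16 = 93.8% (1 − 1/14 = 92.9% for the 14 samples to Week 336). That figure describes one table only. SAP 11.2 makes the scheduled time point the default layout, so the normal-range counts read naturally as by visit, and a low value at Week 96 is counted at Week 96. By-visit counts cannot be added up to the number of participants who were ever low, and the two IgG thresholds are flagged only in the listing.

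**The case against.** The strongest reply is that little is lost. Every rhythm result is listed, about 200 participants were expected in the OLE, and clinically important arrhythmia should reach the adverse event tables. The analysis is descriptive, everyone in the OLE receives evobrutinib, and no hypothesis test depends on this table. The documents do not name atrial fibrillation among the identified or potential risks. This stands as a limit on the weight of the point. It does not close the gap for atrial fibrillation that resolved and was not reported as an adverse event.

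A reader might infer three stronger things that the documents do not support.
- That transient low Ig vanishes from the summaries. It does not: the normal-range counts and time-point displays in SAP 17.8 cover the intermediate visits. That section is also partly redacted, so not every Ig output can be seen.
- That the share of participants hidden by the rule can be stated. It cannot: no per-ECG rate is given, and any figure built on independent ECGs within a person would overstate the gap, because rhythm may persist.
- That the last-value table should be replaced by a worst-category table. Rhythm is a nominal variable. Ranking atrial fibrillation above Other is a choice, and it would hide an Other rhythm in anyone who had both.

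**Conclusion.** The point holds for rhythm. On-treatment atrial fibrillation that resolves before the last ECG is absent, as such, from every planned ECG summary table, and the rule departs without explanation from four other sets of shift tables in the same SAP. It is not lost from the report, because the listing keeps it and the morphology and adverse event tables may reflect it. The illustrative 86% to 87.5% rests on a single affected ECG, equally likely at each scheduled visit; the true miss could be anywhere down to zero. For Ig the gap is confined to a participant-level count, on the reading that the normal-range counts are by visit. This is an inexpensive improvement to safety reporting and affects no efficacy result.

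**What to change.** Keep the last-value rhythm table. Beside it, by treatment group and by OLE baseline rhythm, add the number and percentage of participants with any on-treatment atrial fibrillation and, separately, with any on-treatment Other rhythm, including unscheduled ECGs. A participant with both is counted in both rows, so no ranking is needed. Add a footnote that such counts rise with the number of ECGs per participant.

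As a lesser addition in SAP 17.8, put beside the end-of-OLE shift the number and percentage of participants ever below the normal range on treatment, and ever with IgG below 6 g/L and below 3 g/L.

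The cost is a few sentences in the SAP and minor programming. The data are already collected and listed.
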